8.2.5 Multiplicity

Since there is only one primary PD hypothesis and it is being evaluated with Bayesian methods, no multiplicity adjustment will be made.

8.2.6 Sample Size and Power

If the true SD of the log₁₀ reduction from baseline in plasma HIV-RNA at 168 hours post-dose is 0.25(0.4) for MK-8583, there is ~80% power to yield at least 80% posterior probability that the true mean difference in the plasma HIV-1 RNA reduction from baseline between MK-8583 and placebo is at least 0.5 log₁₀ copies/mL, if the true mean log₁₀ reduction is at least 0.7 log₁₀ (0.8 log₁₀) with N=6 subjects in a Panel. It assumes the historical placebo sample size of 20 with mean reduction of 0 log₁₀ and SD = 0.25. The information of placebo data was from historical placebo data of recent monotherapy studies in HIV-1 subjects (MK-0518 Protocol 004, MK-1439 Protocol 005, MK-6186 Protocol 007, and MK-1972 Protocol 003). The SD of MK-8583 is estimated based on MK-8591 Protocol 003 and MK-8507 Protocol 003 studies (SD ranges from 0.24 to 0.4).

A posterior probability threshold P%=80% is chosen. A favorable posterior probability threshold is defined when the true mean HIV-1 reduction > 0.5 log [relative to Placebo] is >P%; there is relatively low probability of a favorable outcome when the true mean reduction is < 0.5 log₁₀ copies/mL (about 20% or less) and relatively high probability for favorability when the true mean reduction is > 0.7 log₁₀ copies/mL (about 80% or more), assuming a true SD = 25%.

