2.2 Trial Diagram

The trial design is depicted in [Figure 1](#) and [Table 1](#).

[figure not shown]

Figure 1 Trial Design Diagram

Table 1 Dose Plan

Panel ^a	Dose ^b
Panel A	100 mg
Panel B	≤ 150 mg
Panel C ^c	≤ 150 mg

^a In each panel, 6 subjects will receive a single dose of MK-8583.

^b The dose administered in Panels B and C will be determined following review of safety, PK, and viral load data from the previous panel(s) and will not exceed 150 mg. At least approximately 30-40 days will separate the administration of doses between panels to allow time for review of the previous panel safety, PK and viral load data.

^c A decision to enroll Panel C will be made upon completion of the previous panels and review of safety, PK, and viral load data.

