4.2.3.3 Pharmacodynamic Endpoints

A PD endpoint of ≥ 0.5 log₁₀ suppression of HIV-1 RNA from baseline on Day 7, relative to historical placebo data, will be used. This target is consistent with prior monotherapy proof-of-concept studies of NRTIs, including TDF 300 mg daily, which has proven long-term efficacy both as treatment and prevention of HIV infection [4] [10]. An endpoint at 7 days was set based on these published results with daily TDF monotherapy, but also with the expectation that a weekly drug will need to deliver persistent VL suppression throughout the duration between doses.

A posterior probability threshold $P\%=80\%$ is chosen. A favorable posterior probability threshold is defined when the true mean HIV-1 reduction $> 0.5 \log$ [relative to Placebo] is $>P\%$; there is relatively low probability of a favorable outcome when the true mean reduction is $< 0.5 \log_{10}$ copies/mL (about 20% or less) and relatively high probability for favorability when the true mean reduction is $> 0.7 \log_{10}$ copies/mL (about 80% or more), assuming a true $SD = 25\%$.

Based on the long half-life of the active moiety TFV-DP, changes in VL may be assessed through 28 days for subjects who do not initiate follow-on ART. Additionally, the kinetics of VL reduction versus dose and exposure will also be determined.

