7.1.5.5 Trial Design/Dosing/Procedures Modifications Permitted within Protocol Parameters

This is a Phase I assessment of MK-8583 in humans, and the PK, PD and safety profiles of the compound is still being elucidated. This protocol is written with some flexibility to accommodate the inherent dynamic nature of Phase I clinical trials. Modifications to the dose, dosing regimen and/or clinical or laboratory procedures currently outlined below may be required to achieve the scientific goals of the trial objectives and/or to ensure appropriate safety monitoring of the trial subjects.

As such, some alterations from the currently outlined dose and/or dosing regimen may be permitted based on newly available data, but the maximum daily dose may not exceed those currently outlined in the protocol.

- Repeat of or decrease in the dose of the trial drug administered
- Entire panel(s) may be omitted
- Instructions to take trial drug with or without food or drink may also be modified based on newly available data
- Modification of the PK/PD sample processing and shipping details based on newly available data
- Decrease in the length of post-dose PK/PD sample collection

The PK/PD sampling scheme currently outlined in the protocol may be modified during the trial based on newly available PK or PD data (e.g., to obtain data closer to the time of peak plasma concentrations). If indicated, these collected samples may also be assayed in an exploratory manner for metabolites and/or additional pharmacodynamic markers.

Up to additional 50 mL of blood may be drawn for safety, PK, and/or PD analyses. The total blood volume withdrawn from any single subject will not exceed the maximum allowable volume during his/her participation in the entire trial (Section 12.3).

The timing of procedures for assessment of safety procedures (e.g., vital signs, ECG, safety laboratory tests, etc.) currently outlined in the protocol may be modified during the trial based on newly available safety, tolerability, pharmacokinetic or pharmacodynamic data (e.g., to obtain data closer to the time of peak plasma concentrations). Additional laboratory safety tests may be added to blood samples previously drawn to obtain additional safety information (e.g., adding creatinine kinase to serum chemistry panel that was already drawn). These changes will not increase the number of trial procedures for a given subject during his/her participation in the entire trial.

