Primary Objective (Pharmacodynamics): The log₁₀ plasma HIV-RNA (copies/mL) measurements from subjects in all panels will be pooled and analyzed based on a longitudinal data analysis model containing fixed effects for dose level, time (pre-dose, 168 hrs post-dose) and dose level by time interaction, and a random effect for patient. The change from baseline for each dose level at 168 hours post-baseline will be estimated from this model. A posterior distribution for the true mean change from baseline at 168 hours will be generated for each dose level using flat priors under a normal likelihood assumption. Historical placebo data from recent monotherapy studies in HIV-1 subjects (MK-0518 Protocol 004, MK-1439 Protocol 005, MK-6186 Protocol 007, and MK-1972 Protocol 003) will be separately analyzed based on a longitudinal data analysis model containing fixed effects for study and time (pre-dose, 168 hours post-dose), and a random effect for patient. The change from baseline for placebo at 168 hours post-baseline will be estimated from this model, and a posterior distribution for the true mean change from baseline at 168 hours will be generated using flat priors under a normal likelihood assumption. Using the posterior distributions for each dose level and placebo, the posterior distribution of the true mean difference between each dose level and placebo will be generated, and the posterior probability that the true mean difference in the log₁₀ plasma HIV-1 RNA reduction from baseline between MK-8583 and placebo is at least 0.5 log₁₀ copies/mL will be calculated. An 80% posterior probability for at least one dose level that also exhibits an acceptable safety and tolerability profile will satisfy the primary PD hypothesis.

Power

If the true SD of the log₁₀ reduction from baseline in plasma HIV-RNA at 168 hours post-dose is 0.25(0.4) for MK-8583, there is ~80% power to yield at least 80% posterior probability that the true mean difference in the plasma HIV-1 RNA reduction from baseline

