mean change from baseline at 168 hours will be generated using flat priors under a normal likelihood assumption. Using the posterior distributions for each dose level and placebo, the posterior distribution of the true mean difference between each dose level and placebo will be generated, and the posterior probability that the true mean difference in the log₁₀ plasma HIV-1 RNA reduction from baseline between MK-8583 and placebo is at least 0.5 log₁₀ copies/mL will be calculated. An 80% posterior probability for at least one dose level that also exhibits an acceptable safety and tolerability profile will satisfy the primary PD hypothesis. For each dose level, the posterior probability that the true mean log₁₀ plasma HIV-1 RNA reduction from baseline is at least 0.5 log₁₀ copies/mL will also be calculated. Similar exploratory analyses may be performed using viral load measurements at baseline and specified post-baseline time points.

Secondary (Pharmacokinetics)

Separately for each PK parameter, individual values of TFV-DP in PBMC PK parameters AUC_{0-168hr}, C_{max}, and C_{168hr} from subjects in all panels will be pooled, natural log transformed and analyzed based on a linear model containing a fixed effect for dose level. The 95% confidence intervals for the least squares means by dose level will be constructed on the natural log scale and will reference the t-distribution. Exponentiating the least-squares means and lower and upper limits of these confidence intervals will yield estimates for the population geometric means and confidence intervals about the geometric means on the original scale. The posterior probability that the true GM C_{168hr} PBMC TFV-DP level is $\geq 0.1 \mu\text{M}$ will be calculated for each dose level using flat priors under a normal likelihood assumption. An 80% posterior probability for at least one dose level that also exhibits an acceptable safety and tolerability profile will satisfy the secondary PK hypothesis.

MK-8583 plasma AUC_{0-last}, AUC_{0-inf}, C_{max}, CL/F and V_z/F, and TFV plasma AUC_{0-last}, AUC_{0-inf} and C_{max} will be analyzed in a similar fashion.

Descriptive Statistics

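### Do the 20% and 80% pass rates in 8.2.6 misstate the success rule that accepts any one dose level?

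*Combined protocol and SAP*

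**What the plan says.** Sections 4.2.3.3 and 8.2.6 justify the 80% posterior threshold with two pass rates at an SD of 0.25. At the low end, 8.2.6 says "there is relatively low probability of a favorable outcome when the true mean reduction is < 0.5 log₁₀ copies/mL (about 20% or less"); at the high end, the chance is about 80% or higher once the true mean exceeds 0.7. The power paragraph just before this in 8.2.6 is stated "with N=6 subjects in a Panel". Section 4.2.3.3 repeats the low-end sentence ("there is relatively low probability of a favorable outcome when the true mean reduction is" and so on) without that panel reference.

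The success criterion is in 8.1 and 8.2.4: "An 80% posterior probability for at least one dose level that also exhibits an acceptable safety and tolerability profile" satisfies the primary hypothesis. Each dose level is compared with the same historical placebo posterior. Section 8.2.5 reads: "Since there is only one primary PD hypothesis and it is being evaluated with Bayesian methods, no multiplicity adjustment will be made".

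The number of dose levels is not fixed. Under Table 1, "A decision to enroll Panel C will be made upon completion of the previous panels"; 7.1.5.5 adds "Entire panel(s) may be omitted"; and 5.2.1.2 allows a later panel to repeat a dose.

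**The concern.** A rule that needs only one pass among several dose levels has a higher pass rate than any single dose level. The sentence in 8.2.6 does not say which of the two it describes, and in 4.2.3.3 nothing nearby settles it. Nor do the reasons given in 8.2.5 alter the rate: the single hypothesis can be met by up to three doses, and a Bayesian calculation still has a long-run pass rate, which the plan itself uses to defend its threshold.

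At stake is how a positive result is read. Someone who takes 20% as the most that the primary rule can yield when no dose exceeds the target would understate the chance of calling the trial a success when every dose lies at or just below 0.5.

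**Working it through.** **Inputs, all from 8.2.6 unless noted.** SD 0.25 for MK-8583; 6 subjects per dose level; historical placebo n = 20, mean 0, SD 0.25; margin 0.5 log₁₀; threshold 80%; flat priors and normal likelihood (8.2.4); up to three panels (2.1).

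**One dose level: the plan's own figures.** With flat priors and known variance, a dose passes when its estimated difference from placebo exceeds 0.5 by at least z(0.80) standard errors.

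- SE = √(0.25²/6 + 0.25²/20) = √(0.010417 + 0.003125) = 0.1164
- Cutoff = 0.5 + 0.8416 × 0.1164 = 0.598
- P(pass) = Φ((μ − 0.5)/SE − 0.8416)
- At μ = 0.5: Φ(−0.8416) = 20.0%
- At μ = 0.7: Φ(0.2/0.1164 − 0.8416) = Φ(0.877) = 81.0%

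Both printed figures reproduce. For the other power scenario in 8.2.6 (SD 0.4, true mean 0.8), the SE is 0.1726 and the pass rate is 81.5%, against the stated figure of about 80%.

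**At least one of K distinct dose levels.** The dose comparisons share the placebo mean, so they are correlated: 0.003125/(0.010417 + 0.003125) = 0.231. Conditioning on the placebo error z,

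P(any pass) = 1 − E_z[ ∏ Φ((0.598 + s_p z − μ_k)/s_a) ], with s_p = 0.25/√20 and s_a = 0.25/√6.

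| Common true mean | One dose | Two doses | Three doses |
|---|---|---|---|
| 0.40 | 4.4% | 8.4% | 12.0% |
| 0.45 | 10.2% | 18.5% | 25.3% |
| 0.50 | 20.0% | 34.0% | 44.4% |
| 0.70 | 81.0% | 94.5% | 98.0% |

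Ignoring the shared placebo would give 1 − 0.8² = 36.0% and 1 − 0.8³ = 48.8% at 0.50. Simulation with estimated variances and t-type posteriors gives about 34% and 44% at 0.50, and about 94% and 98% at 0.70, so the known-variance shortcut does not drive the result. With SD 0.4 the rates at 0.50 are 35% and 47%.

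**When does the any-dose rate pass 20%?** With equal true means, it does so above about 0.456 for two doses and about 0.433 for three. With unequal true means (illustrative values):

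| True means | P(any pass) |
|---|---|
| 0.5, 0.4 | 22.9% |
| 0.5, 0.4, 0.3 | 23.1% |
| 0.5, 0.4, 0.4 | 25.5% |
| 0.45, 0.40 | 13.7% |
| 0.45, 0.40, 0.35 | 14.8% |

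**Repeated dose.** The model in 8.2.4 has an effect for dose level, not for panel. Two panels at one dose form a single group of 12, whose rate at 0.5 is still 20.0%.

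**The case for a change.** The strongest case for a change is that the plan chose to defend a Bayesian threshold with frequentist rates, and so owes the reader those rates for the rule that actually decides success. Read as a statement about that rule, the 20% ceiling is not true for every true mean below 0.5: three distinct doses at 0.45 give 25.3%, and doses just under 0.5 approach 34% or 44%. Wording would cure it at no cost in subjects or analyses.

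The arithmetic stands, and so does the observation that no section reports the any-dose rate and that 4.2.3.3 lacks the panel reference. What does not stand is that the printed figures mislead in their setting. Section 8.2.6 has just given power per panel of six. The sentence speaks of one true mean and one SD, and it defines a favourable outcome by one posterior probability crossing the threshold, which 8.2.4 computes separately for each dose level. The high-end statement has no discrepancy at all, since the any-dose rates of 94.5% and 98.0% satisfy it.

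The low-end excess is largest when several distinct doses share a true mean very close to 0.5. Section 4.1.2 describes intracellular exposure as rising roughly in proportion to dose, and 4.2.2 allows later doses to go up or down from 100 mg, so equal true means at different doses are not the natural default.

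**Conclusion.** No change is needed. The 20% and 80% figures are correct for a single dose level of six subjects, and 8.2.6 can fairly be read that way. The missing any-dose rate is a gap that an analyst fills from the plan's own inputs: at most about 34% for two distinct doses or 44% for three when every true mean is exactly 0.5, and about 23% for the ordered cases 0.5/0.4 and 0.5/0.4/0.3. These figures assume SD 0.25, 20 placebo subjects and distinct doses, and they ignore the safety condition. That condition, an omitted panel or a repeated dose would lower them; an SD of 0.4 would raise the boundary values to 35% and 47%.

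An open-label Phase Ib proof-of-concept trial with an openly declared absence of adjustment can accept such a rate. Each dose level's posterior probability is calculated in any case, so a reader of the results can see how many doses were tried and how clearly each passed. Reporting the any-dose rate would alter neither the threshold, model, sample size and analysis nor the decision on any given data.

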9.0 LABELING, PACKAGING, STORAGE AND RETURN OF CLINICAL SUPPLIES

9.1 Investigational Product

The investigator shall take responsibility for and shall take all steps to maintain appropriate records and ensure appropriate supply, storage, handling, distribution and usage of investigational product in accordance with the protocol and any applicable laws and regulations.

Clinical Supplies will be provided by the Sponsor as summarized in [Table 9](#).

Clinical supplies will be packaged to support enrollment and replacement subjects as required. When a replacement subject is required, the Sponsor or designee needs to be contacted prior to dosing the replacement supplies.

Table 9 Product Descriptions

Product Name & Potency	Dosage Form	Source/Additional Information
MK-8583 10 mg	Capsule	Provided centrally by the Sponsor
MK-8583 100 mg	Capsule	Provided centrally by the Sponsor

9.2 Packaging and Labeling Information

Clinical supplies will be affixed with a clinical label in accordance with regulatory requirements.

Subjects will receive open label single doses dispensed from supplies packaged in bulk open label bottles. No kitting is required.

9.3 Clinical Supplies Disclosure

This trial is open-label; therefore, the subject, the trial site personnel, the Sponsor and/or designee are not blinded. Treatment (name, strength or potency) is included in the label text; random code/disclosure envelopes or lists are not provided.

9.4 Storage and Handling Requirements

Clinical supplies must be stored in a secure, limited-access location under the storage conditions specified on the label.

Receipt and dispensing of trial medication must be recorded by an authorized person at the trial site.

Clinical supplies may not be used for any purpose other than that stated in the protocol.

9.5 Discard/Destruction>Returns and Reconciliation

The investigator is responsible for keeping accurate records of the clinical supplies received from the Sponsor or designee, the amount dispensed to and returned by the subjects and the amount remaining at the conclusion of the trial. For all trial sites, the local country Sponsor personnel or designee will provide appropriate documentation that must be completed for drug accountability and return, or local discard and destruction if appropriate. Where local discard and destruction is appropriate, the investigator is responsible for ensuring that a local discard/destruction procedure is documented.

10.0 ADMINISTRATIVE AND REGULATORY DETAILS

10.1 Confidentiality

10.1.1 Confidentiality of Data

By signing this protocol, the investigator affirms to the Sponsor that information furnished to the investigator by the Sponsor will be maintained in confidence, and such information will be divulged to the institutional review board, ethics review committee (IRB/ERC) or similar or expert committee; affiliated institution and employees, only under an appropriate understanding of confidentiality with such board or committee, affiliated institution and employees. Data generated by this trial will be considered confidential by the investigator, except to the extent that it is included in a publication as provided in the Publications section of this protocol.

10.1.2 Confidentiality of Subject Records

By signing this protocol, the investigator agrees that the Sponsor (or Sponsor representative), IRB/ERC, or regulatory authority representatives may consult and/or copy trial documents in order to verify worksheet/case report form data. By signing the consent form, the subject agrees to this process. If trial documents will be photocopied during the process of verifying worksheet/case report form information, the subject will be identified by unique code only; full names/initials will be masked prior to transmission to the Sponsor.

By signing this protocol, the investigator agrees to treat all subject data used and disclosed in connection with this trial in accordance with all applicable privacy laws, rules and regulations.

10.1.3 Confidentiality of Investigator Information

By signing this protocol, the investigator recognizes that certain personal identifying information with respect to the investigator, and all subinvestigators and trial site personnel, may be used and disclosed for trial management purposes, as part of a regulatory submissions, and as required by law. This information may include:

1. name, address, telephone number and e-mail address;
2. hospital or clinic address and telephone number;
3. curriculum vitae or other summary of qualifications and credentials; and
4. other professional documentation.

Consistent with the purposes described above, this information may be transmitted to the Sponsor, and subsidiaries, affiliates and agents of the Sponsor, in your country and other countries, including countries that do not have laws protecting such information. Additionally, the investigator's name and business contact information may be included when reporting certain serious adverse events to regulatory authorities or to other investigators. By signing this protocol, the investigator expressly consents to these uses and disclosures.

If this is a multicenter trial, in order to facilitate contact between investigators, the Sponsor may share an investigator's name and contact information with other participating investigators upon request.

10.1.4 Confidentiality of IRB/IEC Information

The Sponsor is required to record the name and address of each IRB/IEC that reviews and approves this trial. The Sponsor is also required to document that each IRB/IEC meets regulatory and ICH GCP requirements by requesting and maintaining records of the names and qualifications of the IRB/IEC members and to make these records available for regulatory agency review upon request by those agencies.

10.2 Compliance with Financial Disclosure Requirements

Financial Disclosure requirements are outlined in the US Food and Drug Administration Regulations, Financial Disclosure by Clinical Investigators (21 CFR Part 54). It is the Sponsor's responsibility to determine, based on these regulations, whether a request for Financial Disclosure information is required. It is the investigator's/subinvestigator's responsibility to comply with any such request.

The investigator/subinvestigator(s) agree, if requested by the Sponsor in accordance with 21 CFR Part 54, to provide his/her financial interests in and/or arrangements with the Sponsor to allow for the submission of complete and accurate certification and disclosure statements. The investigator/subinvestigator(s) further agree to provide this information on a Certification/Disclosure Form, commonly known as a financial disclosure form, provided by the Sponsor. The investigator/subinvestigator(s) also consent to the transmission of this information to the Sponsor in the United States for these purposes. This may involve the transmission of information to countries that do not have laws protecting personal data.

